12.2.1 Analysis Sets

12.2.1.1 Safety Set

The Safety Analysis Set will include all subjects who received study medication. The Safety Analysis Set will be used for demographic and baseline characteristics, and safety summaries.

12.2.1.2 Full Analysis Set

All efficacy analyses will be performed on the Full Analysis Set (FAS). The FAS will be the main population for efficacy. The FAS will consist of all randomized subjects that have received at least one dose of investigational product.

12.2.1.3 Per-Protocol Analysis Set

The Per-Protocol (PP) Analysis Set is defined as all subjects in the FAS that have appropriate exposure to study medication for the 12-week treatment period and without any major protocol deviations that may impact primary efficacy analysis. The set of major protocol deviations and the range of treatment compliance percentage required will be finalized prior to database lock. If a subject withdrew from the study prematurely without Week 12 data to assess the primary and/or key secondary endpoints, he or she may be excluded from the PP Analysis Set.

12.2.1.4 Pharmacokinetic Analysis Set

The PK Analysis Set will include all subjects who received investigational product with all evaluable PK data appropriate for the evaluation of interest (without major protocol deviations or violations that would have an impact on the absorption, distribution, metabolism, or excretion of investigational product). The PK analysis set will be used for analysis of PK endpoints.

12.2.2 Analysis of Demographics and Other Baseline Characteristics

Demographic and baseline characteristics will be summarized for the Safety Analysis Set and the Full Analysis Set. Summary statistics (e.g., number of subjects, mean, median, standard deviation, and range) will be generated for continuous variables and the number and percentage of subjects within each category will be presented for categorical variables.

12.2.4 Safety Analysis and Endpoints

Safety and tolerability of the investigational products will be assessed by collection and review of AEs, laboratory parameters, vital signs, and ECG parameters throughout the duration of the study. Safety analysis will involve examination of the descriptive statistics and individual subject listings for the Safety Analysis Set for any effects of study treatment on clinical tolerability and safety.

All AEs will be coded using MedDRA. Data will be summarized using preferred term and primary system organ class.

AE summaries will include the overall incidence (by system organ class and preferred term), events by maximum intensity, event by relationship to study treatment, events leading to discontinuation of investigational product, and SAEs. Laboratory parameters (hematology, chemistry, and urinalysis), vital signs, and ECG will be summarized descriptively by treatment.

12.3 Interim Analysis

No formal interim analysis is planned.

12.4 Determination of Sample Size

Sample size estimation is based on the proportion of subjects meeting target. Calculation of the sample size based on these assumptions is as follows:

[Hypothesis]

$$H_0 : p_t - p_c \leq 0 \text{ vs } H_1 : p_t - p_c > 0$$

$$n = \frac{(Z_\alpha + Z_\beta)^2(p_t(1-p_t) + p_c(1-p_c))}{(p_t - p_c)^2}$$

Where p is the estimated proportion for each group expressed as the proportion of subjects who achieve sUA <5.0 mg/dL at Day 84 (Visit 8), p_t is the proportion of a test group, and p_c is the proportion of a control group. The values Z_α and Z_β represent values of the standard normal distribution that correspond to a type I error rate of $\alpha=0.025$ and a type II error rate of $\beta=0.2$. Evaluable subjects per study group is determined using estimates of $p_t=0.80$ and $p_c=0.47$, and directly computed values of $Z_\alpha=1.96$ and $Z_\beta=0.84$. Assuming a dropout rate of 20%, 38 subjects per study group are needed to assess the efficacy of LC350189 in an evaluable population of 30 subjects per study group.

The size of the control population is based on the FACT trial (Becker et al 2005a), in which a post hoc analysis of sUA at final visit showed sUA <5 mg/dL in 118/249 (47%) patients treated with febuxostat 80 mg.

Power	Alpha, one-sided	P (test)	P (control)	N (per group)	N (Including drop-out 20%)
80%	0.025	0.80	0.47	30	38

Originally, sample size was calculated compared to the active control group in previous protocol versions. Although a major modification is made to eliminate the active control group, the sample size of each test and placebo group is not changed because the proportion of meeting target is very low in the placebo group when referring other studies and sample size calculation comparing to placebo which is less than 10 subjects per group gives insufficient number for dose selection. Therefore, the sample size is not changed upon elimination of the active control group and maintained 30 subjects per group (38 including drop-out rate 20%) to be sufficient for dose selection and exploratory purpose.

The power when compared to placebo group with the current sample size is calculated more than 99% as follows.

Power	Alpha, one-sided	P (test)	P (placebo)	N (per group)	N (Including drop-out 20%)
>99.9%	0.025	0.80	0.1	30	38

P(placebo) is considered 0.1 based on the below two studies. Although cut-off level of sUA level and assessment time is different in this study, proportion in placebo is assumed conservatively up to 10%.

Study	Endpoint	N	P(placebo)(%)
TMX-00-004 (Becker et al 2005b)	sUA level <6.0 mg/dl at Day 28	35	0%
APEX study (Schumacher et al 2008)	sUA level <6.0 mg/dl at Week 28	99	1%

Since the comparisons will be done sequentially using a closed testing procedure with pre-specified order, no multiplicity adjustment is planned for multiple comparisons.

In this study, a total of 152 subjects, not including those already assigned to the active control group, will be randomized to 4 groups, 114 subjects to three different test doses of LC350189 (38 subjects to each dose) and 38 subjects to placebo (dropout rate of 20%).

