5.0 STUDY OBJECTIVES

5.1 Primary Objective

- To assess the efficacy of LC350189 in terms of sUA level <5 mg/dL at Week 12 (Day 84) to find therapeutic dose of LC350189.

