### 8.1. Analysis of Efficacy Endpoints

The efficacy endpoints of this study are specified in Sections [3.2.1](#), [3.2.2](#), and [3.2.4](#) of this SAP.

All endpoints will be summarized descriptively and will be compared to placebo using descriptive statistics.

Proportions will be analyzed using the Cochran-Mantel Haenszel (CMH) test adjusted by following stratification factors: 1) tophi status at Visit 1, and 2) sUA (level <9.8 mg/dL or  $\geq 9.8$  mg/dL) at Visit 4. The Wald asymptotic 95% confidence limit will be calculated for the risk difference point estimate for pairwise comparisons between each dose group and placebo in pre-specified order of 200 mg versus placebo, 100 mg versus placebo and 50 mg versus placebo; however, if the data suggest and warrant it, the continuity correction adjusting for the difference between the normal approximation and the binomial distribution will be applied. Subgroup analyses of proportions of subjects with sUA level < 5.0 mg/dL (and 6.0 mg/dL as well) will be performed by above stratification factors.

Change and percent change from baseline will be analyzed with an analysis of covariance (ANCOVA) model, including treatment, sUA and tophi strata at screening, and baseline values of the dependent variable as a covariate.

As this is not a rigorous confirmatory trial, no multiplicity adjustment is planned for multiple treatment comparisons or multiple endpoints.

Dropouts will be treated according to non-responder imputation (NRI).

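### The trial is sized and titled for dose finding, but no dose-versus-dose estimate, dose-response model or dose-selection criterion is pre-specified, and no calculation supports the claim that 30 per group is enough to select a dose.

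*Protocol*

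**What the plan says.** - **Objective.** The title calls the study dose finding. Protocol 5.1, repeated in SAP 2.1, gives the purpose of the primary assessment (sUA below 5 mg/dL at Day 84) as "to find therapeutic dose of LC350189".
- **Primary inference.** Protocol 12.2.3 and SAP 8.1 plan a CMH test and Wald 95% limits for the risk difference, for "pairwise comparisons between each dose group and placebo in pre-specified order": 200 mg, then 100 mg, then 50 mg. Change in sUA is analysed by ANCOVA with treatment as a factor. Everything else on efficacy is descriptive by group. SAP section 10 lists, plots and summarises PK and PD by treatment.
- **Sample size.** Protocol 12.4 derives 30 per group from response rates of 0.80 for a test group and 0.47 for the control. The control rate comes from "118/249 (47%) patients treated with febuxostat 80 mg", the arm that version 5.0 removed. The protocol then says that sizing against placebo would need fewer than 10 per group, too few for dose selection, so the size is "maintained 30 subjects per group (38 including drop-out rate 20%) to be sufficient for dose selection and exploratory purpose". SAP 4.1 repeats this. The only power figure for the current design is above 99.9% for 0.80 against a placebo rate of 0.10.
- **Dose modelling.** The one mention, in Protocol 4.4, concerns phase I data used to pick the doses for this trial.

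**The concern.** Dose selection is both the stated purpose of the trial and the stated reason for its size, but the primary tests answer a different question: whether each dose differs from placebo. With placebo response taken as at most 10%, a dose can beat placebo comfortably and still be well short of another dose.

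If two or three doses succeed, the choice among them rests on by-dose summaries read without any criterion fixed in advance. The criterion could then be shaped by the unblinded results. The reader of the report would also have no planned interval showing how uncertain the differences between doses are.

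**Working it through.** **Inputs from the documents.** One-sided alpha 0.025 (z = 1.96), beta 0.2 (z = 0.84), test rate 0.80, former control rate 0.47, placebo rate 0.10, dropout 20%, 30 evaluable and 38 randomised per group (Protocol 12.4); dropouts counted as non-responders (Protocol 12.2.3, SAP 8.1).

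**Assumption.** The documents give one test-group rate, 0.80, and none by dose. I take 0.80 for the better dose and vary the other.

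**1. The plan's own figures reproduce.**
n = (1.96 + 0.84)² × (0.80×0.20 + 0.47×0.53) / 0.33² = 29.45, rounded up to 30. With dropout, 30/0.8 = 37.5, rounded up to 38. Power for 0.80 vs 0.10 at 30 per group exceeds 99.9%. The same formula against placebo gives 4 per group, consistent with the protocol's fewer than 10. The arithmetic is sound. Read as a comparison of two doses, the 30 gives 80% power only for a gap of about 33 points.

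**2. Do the placebo comparisons separate the doses?** Simulation at 30 per group, counting trials in which the lower Wald limit is above zero for all three doses, placebo 0.10:
- true rates 0.80/0.70/0.60: all three win with probability 0.99;
- true rates 0.80/0.60/0.40: 0.82.

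A weak low dose can fail: 0.32 vs 0.10 at 38 per group has 69% power.

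**3. What can be said between two doses?**
SE = √{[p1(1−p1) + p2(1−p2)]/n}; half-width = 1.96 × SE; power = Φ(|p1−p2|/SE − 1.96).

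Example, 0.80 vs 0.60 at n = 38: SE = √(0.40/38) = 0.1026; half-width 0.201; power Φ(1.949 − 1.96) = 0.496.

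The ranking column is the exact binomial probability that the better dose shows strictly more responders.

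| Assumed rates | n | Half-width (points) | Power | Better dose ranked first |
|---|---|---|---|---|
| 0.80 vs 0.70 | 38 | 19.3 | 17% | 0.81 |
| 0.80 vs 0.60 | 38 | 20.1 | 50% | 0.965 |
| 0.80 vs 0.40 | 38 | 20.1 | 97% | >0.99 |
| 0.80 vs 0.70 | 30 | 21.8 | 14% | 0.77 |
| 0.80 vs 0.60 | 30 | 22.6 | 41% | 0.94 |
| 0.80 vs 0.47 | 30 | 22.9 | 81% | >0.99 |
| 0.64 vs 0.48 | 38 | 22.0 | 30% | 0.90 |

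The last row is 0.80 vs 0.60 with 20% dropout in both groups counted as failures (0.80×0.8 and 0.60×0.8): SE = √(0.48/38) = 0.1124. This is closest to the planned primary analysis. The n = 30 rows are evaluable subjects only; the other n = 38 rows assume no dropout.

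**The case against.** The strongest reply is that a phase II dose choice need not rest on significance between doses. SAP 8.1 says the trial is not rigorously confirmatory. The plan yields, for every dose, a risk difference against placebo with its interval, response at both sUA thresholds, an ANCOVA of sUA change, trough PK and safety. If the dose is picked by observed ranking, the table shows the better one comes first about 90 to 97% of the time at gaps of 16 to 20 points. The fixed testing order can also screen out a weak low dose.

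Most of this stands, and it rules out several stronger readings:
- **That 30 per group has been shown insufficient.** The documents set no criterion for sufficiency, so nothing exists for it to fail.
- **That the plan expects every dose to beat placebo easily.** No dose-specific rates are given, and Protocol 4.4 places the expected therapeutic dose between 100 and 200 mg, with 50 mg as the minimum.
- **That the planned output is silent on dose choice.** The by-dose results above bear on it.
- **That a trend test would settle the matter through greater power.** At assumed rates of 0.32/0.48/0.64 it has about 80% power against 30% for each adjacent pair, but those are different effect sizes: 200 vs 50 mg alone has 84%. With 0.32/0.64/0.64 the trend test (scores 50/100/200) still rejects about 70% of the time, although the top two doses are equal.

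What the reply does not supply is a rule. Nothing says that ranking is the criterion, which outcome it would use, or how close two doses may be before the choice turns on something else.

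**Conclusion.** The point holds in this form: the analysis plan contains no dose-versus-dose estimate, dose-response model or selection criterion for a trial whose objective is to find a dose, and the sample-size statement on dose selection has no calculation behind it. The sample-size arithmetic itself is correct, and the sufficiency statement is unsupported, not refuted.

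The delivered precision between doses is roughly ±19 to 23 points. Whether that is adequate depends on the true gaps, which are assumed here: a 40-point gap is easily seen, a 20-point gap is a coin toss for formal separation (less once dropouts count as failures) but usually ranked correctly, and a 10-point gap is poorly resolved by either route. This should be changed, but it does not threaten the validity of the placebo comparisons.

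**What to change.** 1. **SAP 8.1, estimation between doses.** Add strata-adjusted risk differences with 95% confidence intervals for 100 vs 50, 200 vs 100 and 200 vs 50 mg on the primary endpoint.
2. **SAP 8.1, one dose-response model.** Pre-specify a model of the primary endpoint over placebo and the three doses that is defined at dose zero, such as an Emax model or a logistic model on log(dose + a stated offset). A model linear in plain log-dose cannot include placebo. Report estimated response with 95% confidence interval at each dose, as estimation and not as a test that names a dose.
3. **Selection criterion.** Have the sponsor record, before unblinding, the criterion it will use to select a dose. Its content is for the sponsor.
4. **Protocol 12.4 and SAP 4.1.** Replace the sufficiency statement with the precision between doses (about ±19 to 23 points) or the probability of correct ranking, with the assumed rates stated.

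Cost: one additional model, a few tables and a less favourable sentence on sample size. No additional patients, visits or samples.

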13.0 QUALITY CONTROL AND QUALITY ASSURANCE

13.1 Monitoring

The study will be monitored by a qualified monitor.

Monitoring visits to the study site(s) will be made periodically during the study to ensure that all aspects of the protocol and GCP are followed, eCRFs are completed correctly and completely, and drug accountability is monitored. The Monitor should visit the study site (physically or remotely) at least once before First Subject First Visit (FSFV) for an Initiation Visit, at least once during the clinical part of the study, and at least once after Last Subject Last Visit (LSLV). Furthermore, the Monitor must be available for discussions by telephone.

The Sponsor or delegate may assign additional Clinical Research Associates (CRAs)/Monitors on an ad hoc basis for training purposes and to meet required timelines. In addition, if study timelines are modified for any reason, *e.g.*, delays in recruitment or accelerated enrollment, the Sponsor or delegate may use additional CRAs at its discretion to ensure study expectations are met.

The Monitor must be given direct access to source documents, such as original documents, data, and records. Direct access includes permission to examine, analyze, and verify any record(s) and report(s) that are important to evaluation of the clinical study. The study will be monitored to verify integrity and validity of the data. Monitors will follow a study-specific Monitoring Plan.

Additional quality control (QC) monitoring of the clinical study for protocol and GCP compliance will be conducted periodically by qualified staff of the Sponsor or delegate.

13.2 Protocol Deviations

The Investigator should not deviate from the protocol, except where necessary to eliminate an immediate hazard to study subjects. Should other circumstances arise that will require deviation from protocol-specified procedures, unless there is an emergency or immediate need, the Investigator should contact the Medical Monitor and Sponsor to review and discuss the implications of the deviation and determine the appropriate course of action. Any deviation must be documented, stating the reason and date, the action taken, and the impact for the subject and/or the study. The documentation must be kept in the ISF and the Trial Master File.

14.0 ETHICAL ASPECTS OF THE STUDY

This study will be conducted in accordance with the Protocol, the International Council for Harmonization of Technical Requirements for Pharmaceuticals for Human Use (ICH), Guideline for Good Clinical Practice: Consolidated Guidance (E6) and applicable regulatory requirements including clinical research guidelines established by the Basic Principles defined in the U.S. 21 CFR Parts 50, 56, and 312 and the principles enunciated in the Declaration of Helsinki (prior to 2000).

14.1 Institutional Review Board and/or Independent Ethics Committee

Prior to commencement of the study, the protocol, any amendments, subject information/ ICF, any other written information to be provided to the subject, subject recruitment procedures, information about payments and compensation available to subjects if not mentioned in the subject information, the Investigator's current curriculum vitae and/or other documentation evidencing qualifications, and other documents as required by the local IEC/ IRB should be submitted. Written approval/favorable opinion must be obtained from IEC/IRB prior to commencement of the clinical study start.

The Investigator or designee shall provide to Sponsor or its designee a copy of the written and dated approval/favorable opinion by the applicable IRB/IEC.

During the study, the Investigator must promptly report the following to the IEC/IRB: Updates to the Investigator Brochure, unexpected SAEs where a causal relationship cannot be ruled out, substantial amendments to the protocol, non-substantial amendments, deviations to the protocol implemented to eliminate immediate hazards to the subjects, new information that may affect adversely the safety of the subjects or the conduct of the study (including new risk/benefit analysis in case it will have an impact on the planned follow-up of the subjects), annually written summaries of the study status, and other documents as required by the local IEC/IRB.

Substantial amendments must not be implemented before approval/favorable opinion, unless necessary to eliminate hazards to the subjects.

The Investigator must maintain an accurate and complete record of all submissions made to the IEC/IRB. The records should be filed in the Investigator's Study File and copies must be provided to the Sponsor.

14.2 Regulatory Authorities

Regulatory Authorities will receive the clinical study application, protocol, amendments to the protocol, reports on SUSARs and other applicable SAEs and the integrated clinical study report according to national regulations.

14.3 Responsibilities of the Investigator

The Investigator will conduct this clinical study in compliance with all applicable national, state, local or regional laws and regulatory requirements of the countries in which the clinical study is

performed. The Investigator will align his or her conduct in accordance with the “Responsibilities of the Investigator”.

The Investigator may appoint such other individuals as he/she may deem appropriate as Sub-Investigators to assist in the conduct of the Clinical Study in accordance with the Clinical Study Protocol. All Sub-Investigators shall be timely appointed and listed, and will be supervised by and under the responsibility of the Investigator, and that will be noted in the Delegation of Authority log at the clinical study site. Those Sub-Investigators will have the appropriate documented training in a written training log. The Investigator will provide them with a Clinical Study Protocol and all necessary information. Each Sub-Investigator is fully responsible for fulfilling all of the obligations of an Investigator as identified in 21 CFR 312.60. Thus under 21 CFR 312.3(b), the Investigator and each Sub-Investigator must sign a separate Form FDA 1572 before participating in this study.

In compliance with the Clinical Study Protocol, GCP, and applicable regulatory requirements, the Investigator must permit auditing by or on the behalf of the Sponsor and inspection by applicable regulatory authorities. The Investigator agrees to allow the auditors/inspectors to have direct access to his/her study records for review; being understood that these personnel are bound by professional secrecy and as such will not disclose any personal identity or personal medical information. The Investigator will make every effort to help with the performance of the audits and inspections, giving access to all necessary facilities, data, and documents. As soon as the Investigator is notified of a future inspection by the authorities, he or she will inform the Sponsor or its designee and authorize the Sponsor or its designee to participate in this inspection. Any results and information arising from the inspections by the regulatory authorities will be immediately communicated to the Sponsor. The Investigator shall take appropriate measures required by the Sponsor to take corrective actions for all problems found during the audit or inspections.

Clinical research studies sponsored by the Sponsor are subject to ICH GCP and all the applicable local laws and regulations. The responsibilities imposed on Investigators by the FDA are summarized in the “Statement of Investigators” (Form FDA 1572) or the investigator agreement (device studies), which must be completed and signed before the Investigator may participate in this study.

14.4 Informed Consent

Once signed, the original ICF, subject authorization form (if applicable), and subject information sheet (if applicable) will be stored in the Investigator’s site file. The Investigator must document the date the subject signs the informed consent in the subject’s medical record. Copies of the signed ICF, the signed subject authorization form (if applicable), and subject information sheet (if applicable) shall be given to the subject.

All revised ICFs must be reviewed and signed by relevant subjects or the relevant subject’s legally acceptable representative in the same manner as the original informed consent. The date the revised consent was obtained should be recorded in the subject’s medical record, and the subject should receive a copy of the revised ICF.

